## **6 CONGENITAL ANOMALIES/BIRTH DEFECTS**

Any congenital anomaly/birth defect in a child born to a female partner of a male participant exposed to the study drug should be classified as a serious adverse event, recorded on the Adverse Event eCRF, and reported to the Sponsor immediately (i.e., no more than 24 hours after learning of the event; see [Section 5](#) of Appendix 2).

## Appendix 6 Protocol Amendment History

### Document History

Documents	Dates	Substantial	Region
Version 2 (Amendment 1)	06 December 2018	Yes	China
Version 1 (Original Protocol)	07 August 2018	-	-

1. INTRODUCTION

This document describes the rules and conventions to be used in the presentation and analysis of pharmacokinetic and safety data for Protocol YP40902. It describes the data to be summarized and analyzed, including specifics of the statistical analyses to be performed.

This statistical analysis plan (SAP) is based on protocol version 2.0, dated 10Jan2019.

2. STUDY OBJECTIVES

2.1. PRIMARY OBJECTIVE

The primary objective is to evaluate the pharmacokinetics of baloxavir marboxil and baloxavir after a single oral dose of baloxavir marboxil.

2.2. SECONDARY OBJECTIVES

The secondary objective is to evaluate the safety and tolerability following a single oral dose of baloxavir marboxil.

3. STUDY DESIGN

3.1. GENERAL DESCRIPTION

OVERALL DESIGN

Study Design

This Phase I study is an open-label, randomized, parallel-group, two dose level study in healthy Chinese participants to evaluate the PK, safety, and tolerability of baloxavir marboxil and baloxavir following a single oral administration of baloxavir marboxil.

Treatment Groups and Duration

A total of 32 healthy Chinese participants 16 in each group will be enrolled in the study.

After signing the informed consent, a screening period of up to 28 days is provided to complete the study-related assessments.

During the in-house period, on confirming all the eligibility requirements, the participants will be randomly allocated to one of the two parallel groups, 40 mg or 80 mg of study medication (baloxavir marboxil). The

Document: Roche_YP40902_SAP

Authors: [REDACTED], [REDACTED], [REDACTED]

Version Number: 2.2

Version Date: 06MAR2020

Template No.: CS_TP_BS016 Revision 5

Reference: CS_WI_BS005

Effective Date: 01Apr2018

participants will be admitted to the study center on Day -1 and receive study medication on morning of Day 1. Safety assessments and PK sampling will be carried out at scheduled timepoints. The study medication will be given after an overnight fast of approximately 10 hours followed by a fast of at least 4 hours postdose. Participants will receive standard meals while in the study center and can be discharged at the investigator's discretion on Day 4 after the 72-hour assessments have been completed.

The participants will visit the study center on Days 6, 8, 10, 12, and 15 for PK sampling, safety, and other assessments such as vital signs, ECG, and laboratory test etc.

Length of Study

The total duration of the study for each participant will be up to 6 weeks divided as follows:

- Screening: Up to 4 weeks
- In-house period: Day -1 to morning of Day 4
- Post-dosing and follow-up observation: Days 6, 8, 10, 12, and 15.

Participants will be admitted to the study center on Day -1 and will be discharged approximately 72 hours after the study medication administration.

End of Study

The end of the study is defined as the date when the last observation of the last participant occurs and is expected 14±1 day after the dose administration of last participant, unless the participant withdraws his/her consent or withdraws early due to any other reason.

NUMBER OF PARTICIPANTS

A total of 32 healthy Chinese participants, 16 participants in each group will be enrolled in the study. The number of participants (16 participants for each dose level) is chosen based on practical clinical judgement, the PK variability observed, anticipated drop-rate, and China's regulatory requirement. It is considered that 16 study participants in each group would provide sufficient data to characterize the PK of baloxavir and baloxavir marboxil.

SAMPLE SIZE DETERMINATION

A total of 32 Chinese participants will be enrolled in this study with 16 participants in each group of 40 mg and 80 mg baloxavir marboxil. The number of participants (16 participants for each dose level) is chosen based on practical clinical judgment, the PK variability observed (AUC and C_{max} in Caucasian and Japanese healthy participants), anticipated drop-rate, and China's regulatory requirements.

3.2. SCHEDULE OF EVENTS

Schedule of events can be found in section 1.3, [Table 1](#) of the protocol.

Document:	Roche_YP40902_SAP	Version Number:	2.2
Authors:	[REDACTED], [REDACTED], [REDACTED]	Version Date:	06MAR2020
Template No.:	CS_TP_BS016 Revision 5	Reference:	CS_WI_BS005
Effective Date:	01April2018		

3.3. CHANGES TO ANALYSIS FROM PROTOCOL

1. The all subjects randomized (RND) set is added to include all subjects provided informed consent for this study and are randomized to study medication.
2. The all subjects enrolled set (ENR) is added to include all subjects who provided informed consent for this study.

4. PLANNED ANALYSES

4.1. DATA MONITORING COMMITTEE (DMC)

There will be no DMC for this study.

4.2. INTERIM ANALYSIS

There are no interim analyses planned for this study.

4.3. FINAL ANALYSIS

All final, planned analyses identified in this SAP will be performed by [REDACTED] Biostatistics following sponsor authorization of this statistical analysis plan, and database lock.

5. ANALYSIS SETS

5.1. ALL SUBJECTS ENROLLED SET [ENR]

The all subjects enrolled (ENR) set will contain all subjects who provide informed consent for this study.

5.2. ALL SUBJECTS RANDOMIZED SET [RND]

The all subjects randomized (RND) set will contain all subjects provide informed consent for this study and are randomized to study medication.

Document: Roche_YP40902_SAP

Authors: [REDACTED], [REDACTED], [REDACTED]

Version Number: 2.2

Version Date: 06MAR2020

Template No.: CS_TP_BS016 Revision 5

Reference: CS_WI_BS005

Effective Date: 01April2018

For analyses and displays based on RND, subjects will be classified according to randomized treatment.

5.3. SAFETY ANALYSIS SET [SAF]

The safety analysis set (SAF) will contain all subjects who received at least 1 dose of the study medication, whether prematurely withdrawn from the study or not. Subjects will be grouped by the actual dose regimen they received. All safety analyses will be based on the safety analysis set.

5.4. PK ANALYSIS POPULATION

All participants who receive study medication and who have evaluable PK data with no relevant protocol deviations with respect to the primary PK endpoint will be included in the PK analysis population.

Analyses will be carried out on the PK analysis population.

6. GENERAL CONSIDERATIONS

6.1. SUMMARY STATISTICS

For categorical variables, the population size (N for sample size and n for available data) and the percentage (of available data) for each class of the variable will be presented. Quantitative non-PK variables will be summarized using descriptive statistics, including n (number of subjects with non-missing observations), arithmetic mean, standard deviation (SD), 95% confidence interval (CIs) for the mean, median, minimum, and maximum values.

Summary statistics of plasma PK concentrations will include: n, arithmetic mean, SD, CV%, median, minimum and maximum.

Summary statistics for all plasma PK parameters (except for T_{max}) include: n, geometric mean, geometric CV%, arithmetic mean, SD, CV%, median, minimum, and maximum.

The PK parameter T_{max} will be summarized using n, median, minimum and maximum.

In general, data will be presented for each dose group (baloxavir marboxil 40 mg and 80 mg). An $n \geq 2$ will be

Document: Roche_YP40902_SAP

Authors:

[REDACTED], [REDACTED], [REDACTED]

Version Number: 2.2

Version Date: 06MAR2020

Template No.: CS_TP_BS016 Revision 5

Reference: CS_WI_BS005

Effective Date: 01April2018

required for calculations of descriptive statistics. If $n = 1$, only n , minimum and maximum will be presented.

6.2. PRECISION

Safety variables (i.e., clinical laboratory values, vital signs, and ECG intervals) will be reported to the same precision as the source data. The derived variables (i.e., BMI) will be reported 1 more decimal place than the source data.

All PK concentrations will be reported and analyzed with the same precision as the source data regardless of how many significant figures or decimals the data carry. Derived PK parameters will be rounded for reporting purposes in by-subject listings. The unrounded derived PK data will be considered the source data for the calculation of descriptive statistics. For most derived PK parameters, values will be rounded to 3 significant digits, with the following exceptions:

- Parameters directly derived from source data (e.g., C_{max}) will be reported and analyzed with the same precision as the source data.
- Parameters derived from actual elapsed sample collection times (e.g., T_{max}) will be reported with the same precision as the actual elapsed sampling time value of the source data.

For the reporting and presentation of descriptive statistics and the results of statistical analyses, the following rules for precision will be applied.

Statistic	Precision for Reporting
Counts (n)	None
Percentages (%)	1 decimal place
Mean and difference between means (unadjusted and adjusted)	Actual data + 1 decimal place or digit
Median	Actual data + 1 decimal place or digit
SD	Actual data + 2 decimal place or digit
SE	Actual data + 2 decimal place or digit

Document: Roche_YP40902_SAP

Authors: [REDACTED], [REDACTED], [REDACTED]

Version Number: 2.2

Version Date: 06MAR2020

Template No.: CS_TP_BS016 Revision 5

Reference: CS_WI_BS005

Effective Date: 01April2018

F. Hoffmann-La Roche Ltd and Shionogi & Co., Ltd
PROTOCOL YP40902

Confidence intervals	Actual data + 1 decimal place or digit
Min	Same as actual data
Max	Same as actual data
CV%	1 decimal place
Geometric n	None
Geometric Mean	Actual data + 1 decimal place or digit
Geometric CV%	Actual data + 1 decimal place or digit
Slope	2 decimal places
Ratio between means	2 or 3 decimal places (according to endpoint)
p-values	3 decimal places Note: Any p-value less than 0.001 will be presented as <0.001. Any p value greater than 0.999 will be presented as >0.999.

6.3. REFERENCE START DATE AND STUDY DAY

Study Day will be calculated from the reference start date and will be used to show start/ stop day of assessments and events.

Reference start date is defined as the day of the first dose of study medication, (Day 1 is the day of the first dose of study medication) and will appear in every listing where an assessment date or event date appears.

- If the date of the event is on or after the reference date then:

Study Day = (date of event – reference date) + 1.

- If the date of the event is prior to the reference date then:

Study Day = (date of event – reference date).

Unless otherwise specified, In the situation where the event date is partial or missing, Study Day and any

Document: Roche_YP40902_SAP

Authors: [REDACTED]

Version Number: 2.2

Version Date: 06MAR2020

Template No.: CS_TP_BS016 Revision 5

Reference: CS_WI_BS005

Effective Date: 01Apr2018

corresponding durations will appear missing in the listings.

6.4. BASELINE

Unless otherwise specified, baseline is defined as the last non-missing measurement taken prior to reference start date (including unscheduled assessments). In the case where the last non-missing measurement and the reference start date coincide, that measurement will be considered as baseline, but Adverse Events (AEs) and medications commencing on the reference start date will be considered post-baseline.

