### List of Main Changes in the Amendment:

- Table 1 and Table 1 footnote in Section 1.3: Add drug screen action on Day -1 visit in the table; move weight assessment from Day 1 to Day -1; remove hematology, urinalysis, clinical chemistry test on Day 1; remove HBcAg, HbcAb related tests and contents, add serological test for *syphilis* in the footnote 'l'; remove blood samples for pharmacogenomic testing; update information of ECG testing in the footnote 'f' from "Triplicate 12-lead ECG will be performed at specified timepoints" to "Triplicate 12-lead ECG *can* be performed at specified timepoints if deemed necessary by investigator", also add text "*Timepoints for ECG evaluation from Day 1 are provided in Table 2*".
- Table 2 in Section 1.3: Remove weight, ECG, laboratory tests at pre-dose from administration on Day 1 during the in-house period; remove blood samples for pharmacogenomic testing.
- Section 1.1 and 4.1: Add "*PK sampling*" to the assessments of participants who will visit the study center on Days 6, 8, 10,12, and 15.
- Synopsis and Sections 5.1: Update "body mass index is  $\geq 18.5$  to  $26 \text{ kg/m}^2$ " to "body mass index is  $\geq 18.5$  to  $<26 \text{ kg/m}^2$ " in the inclusion criteria.
- Synopsis and Sections 5.2: Revise "average diastolic blood pressure (40-90 mmHg)" to "average diastolic blood pressure (60-90 mmHg)" in the exclusion criteria.
- Sections 8.2.3: Add information "*Triplicate 12-lead ECG can be performed at specified timepoints if deemed necessary by investigator*".

- Sections 8.7: Remove all pharmacogenomics information in the section and replace with “Pharmacogenomics assessments are not performed in this study”.
- Table 7 in Appendix 4: Remove HBcAb test and add serological test for syphilis.

In addition, minor formatting updates and corrections have been made. Such changes are not listed in this amendment.

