**Table 1 Schedule of Activities**

Cycle/Visit/Week	Screening	In-House					Post-Dosing and Follow-up Observation				
		Day -28 to -2	Day -1	Day 1	Day 2	Day 3	Day 4	Day 6	Day 8	Day 10	Day 15
Day	Day -28 to -2			0	24	48	72	120	168	216	264
Time Relative (h)											336
Visit Window (h)				± 2	± 2	± 2	± 2	± 24	± 24	± 24	± 24
Assessments											
Informed consent a		x									
Demographic data		x									
Medical history		x									
Height		x									
Weight	x	x					x	x			
Drug Screen b	x	x									
Randomization c			x								
Drug Administration			x								
Physical Examination d	x	x	x	x	x	x	x	x	x	x	x
Vital Signs e	x	x	x	x	x	x	x	x	x	x	x
ECG f	x	x	x	x	x	x	x				
Hematology g	x	x		x	x	x	x		x		x
Urinalysis h	x	x		x	x	x	x		x		x
Clinical Chemistry i	x	x		x	x	x	x		x		x
Coagulation test, Thyroid and Lipid profile j	x	x					x				
Pregnancy test k	x	x									x
Serology test l	x										
PK Blood Samples m			x	x	x	x	x	x	x	x	x
Admission		x									
Discharge						x					
Ambulatory visit							x	x	x	x	x
Concomitant medications	x	x	x	x	x	x	x	x	x	x	x
Adverse events n	x	x	x	x	x	x	x	x	x	x	x

eCRF = electronic Case Report Form; GGT = gamma-glutamyl transferase, h = hours; HBsAg = hepatitis B surface antigen; HCV = hepatitis C virus; PK = pharmacokinetic and TSH = thyroid stimulating hormone.

a Written informed consent for participants in the study must be obtained before performing any study-specific screening tests or evaluations.

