**Baloxavir marboxil—F. Hoffmann-La Roche Ltd and Shionogi & Co., Ltd**

Protocol YP40902, Version 2

Page 16 of 74

- b Breath alcohol, urine cotinine, and urine drug screen of (amphetamines, barbiturates, cocaine, opiates, methadone, cannabinoids, and benzodiazepines) will be evaluated.
- c Participants will be randomized to 40 mg or 80 mg baloxavir marboxil in a 1:1 ratio.
- d Complete physical examination will be conducted at screening and brief physical examination will be done at other visits.
- e Vital signs include body temperature, pulse rate, blood pressure, and respiratory rate. Blood pressure and pulse rate should be measured at least 5 minutes after the participant rests in a supine position and on the same arm. Assessment of vital signs should be done prior to blood collection.
- f Triplicate 12-lead ECG *can* be performed at specified timepoints if deemed necessary by investigator. At each timepoint at which triplicate ECGs are required, three individual ECG tracings should be obtained as closely as possible in succession, but no more than 2 minutes apart. The full set of triplicates should be completed in less than 4 minutes. Electrocardiogram should be performed prior to any scheduled vital sign measurements and blood draws. In some cases, it may be appropriate to repeat abnormal ECGs to rule out improper lead placement as contributing to the ECG abnormality. *Timepoints for ECG evaluation from Day 1 are provided in Table 2.*
- g Hematology test parameters include leucocytes, erythrocytes, hemoglobin, hematocrit, platelets, differential count (neutrophils, eosinophils, basophils, monocytes, lymphocytes, other cells).
- h Urinalysis include pH, glucose, protein, and blood (leukocyte). If there is a clinically significant positive result (confirmed by a positive repeated sample), urine sample will be sent to the laboratory for microscopy and culture. If there is an explanation for the positive dipstick results (e.g., menses), it should be recorded and there is no need to perform microscopy and culture.
- i Clinical chemistry test parameters include sodium, potassium, chloride, bicarbonate, glucose (fasting), urea, creatinine, total protein, serum albumin, phosphate, calcium, total and direct bilirubin, alkaline phosphatase, ALT, AST, urate, and LDH.

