**Table 2 Detailed Table of Activities**

Period	Day	Time from administration (h)	Randomization	Drug Administration	Physical Examination	Weight	Vital Signs	ECG	Laboratory Tests	PK Blood Samples
In-House	Day 1	Pre-dose	x		x		x			x
		0		x						
		0.5								x
		1			x					x
		2					x	x		x
		3								x
		4			x		x	x		x
		5								x
		6								x
		8								x
		12			x		x	x		x
		24			x		x	x	x	x
	Day 2	36								x
		48			x		x	x	x	x
		72			x	x	x	x	x	x
Post-Dosing and Follow-up Observation	Day 6	120			x	x	x	x	x	x
	Day 8	168			x		x			x
	Day 10	216			x		x		x	x
	Day 12	264			x		x			x
	Day 15	312			x		x		x	x

ECG =electrocardiogram; h = hours; PK = pharmacokinetics.

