**In-house Period:**

On confirming all the eligibility requirements, the participants will be randomly allocated to one of the two parallel groups, 40 mg or 80 mg of study drug (baloxavir marboxil).

Participants will be admitted to the study center on Day -1. On the morning of Day 1, participants will receive a single 40 mg or 80 mg oral dose of the study drug. The study drug will be administered after an overnight fast of approximately 10 hours. No breakfast will be served in the morning of Day 1. A standard lunch will be provided 4 hours after study drug administration. Safety assessments and PK sampling will be done at scheduled timepoints. See SoA in [Section 1.3](#). Participants will receive standard meals while in the study center and can be discharged at the investigator's discretion on Day 4 after the 72-hour assessments have been completed.

**Post-Dosing and Follow-up Observation:** Participants will visit the study center on Day 6 for post-dosing assessments and *PK sampling*. The participants will visit the study center on Days 8, 10, 12, and 15 for *PK sampling*, the safety and other assessments as specified in SoA.

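### SAP 6.4 sets baseline by calendar date with no pre-dose condition, so a post-dose Day 1 ECG or vital-sign reading can become baseline; every scheduled Day 1 ECG is post-dose

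*SAP*

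**What the plan says.** SAP 6.3 fixes the anchor: "Reference start date is defined as the day of the first dose of study medication". It is a date; no time of dosing enters the definition.

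SAP 6.4 has two parts. The general rule is that "baseline is defined as the last non-missing measurement taken prior to reference start date (including unscheduled assessments" (the parenthesis closes there). The second part covers same-day data: "In the case where the last non-missing measurement and the reference start date coincide, that measurement will be considered as baseline". The rest of that sentence places adverse events and medications that begin on the dosing date after baseline. Neither part mentions dosing time, and SAP 17.4 (ECG) and 17.5 (vital signs) give no definition of their own.

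On the protocol side, section 4.1 has morning dosing: "On the morning of Day 1, participants will receive a single 40 mg or 80 mg oral dose of the study drug". Footnote f to Table 1 says of ECGs: "Timepoints for ECG evaluation from Day 1 are provided in Table 2". Table 2 has no ECG mark in the pre-dose row; its Day 1 ECG marks are at 2, 4 and 12 h. Day 1 vital signs are marked at pre-dose, 2, 4 and 12 h. Table 1 also schedules both on Day -1.

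**The concern.** The same-day clause would be harmless if every dosing-day measurement were taken before the dose. Here most are taken after it, and for ECG all the scheduled ones are. A programmer who matches on date alone and keeps the last record on that date would take the 12 h reading.

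The outputs that depend on this baseline are:
- ECG and vital-sign change from baseline by visit;
- the ECG and vital-sign shift tables;
- the QTcF change classes (above 30, 60 and 90 ms in SAP 17.4);
- the change limbs of the vital-sign criteria in SAP 17.5.1 (systolic 20 mmHg, diastolic 15 mmHg, heart rate 15 bpm, temperature 1.1 °C).

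Vital signs are part of the secondary endpoint in protocol Table 3. ECG is not listed there, but it is a planned safety summary. An on-treatment baseline absorbs any early drug effect into the reference value, so a real change could be understated or missed.

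**Working it through.** The plan states no figure to reproduce. The check reads the schedule and applies the rule to it.

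**Inputs.** From protocol Table 2, with 24 h assigned to Day 2 as in Table 1:
- Post-dose ECG: 2, 4, 12, 24, 48, 72, 120 h = 7 timepoints.
- Post-dose vital signs: 2, 4, 12, 24, 48, 72, 120, 168, 216, 264, 312 h = 11 timepoints.
- Participants: 32 (protocol 9.2).

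The empty pre-dose ECG cell is not a table-reading fault. The Amendment 1 change list agrees with the current table: "Remove weight, ECG, laboratory tests at pre-dose from administration on Day 1 during the in-house period".

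**Step 1. What falls on the dosing date.** A dose given before noon puts the 12 h reading before midnight, so 2, 4 and 12 h all carry the Day 1 date.

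| Measure | Scheduled on Day 1 | Pre-dose | Post-dose |
|---|---|---|---|
| ECG | 3 | 0 | 3 |
| Vital signs | 4 | 1 | 3 |
| Laboratory tests | 0 | 0 | 0 |
| Weight | 0 | 0 | 0 |

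**Step 2. Baseline under each rule.**

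| Measure | Last value on the dosing date | Last value before dosing |
|---|---|---|
| ECG | 12 h post-dose | Day -1 |
| Vital signs | 12 h post-dose | Day 1 pre-dose |
| Laboratory tests, weight | none on Day 1, so Day -1 | Day -1 |

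**Step 3. Post-dose timepoints left after baseline** (total minus those at or before the chosen reading):

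| Reading used as baseline | ECG | Vital signs |
|---|---|---|
| Valid pre-dose value | 7 | 11 |
| 2 h | 7 − 1 = 6 | 11 − 1 = 10 |
| 4 h | 7 − 2 = 5 | 11 − 2 = 9 |
| 12 h | 7 − 3 = 4 | 11 − 3 = 8 |

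With the 12 h reading as baseline, the 12 h change is zero by construction, and the 2 h and 4 h values precede their own baseline. The lost 4 h reading sits at the baloxavir Tmax reported in protocol 2.2. Whichever Day 1 post-dose reading is used, all 7 ECG changes and all 11 vital-sign changes would be taken against an on-treatment value.

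**Step 4. Volume.** With full attendance, Day 1 supplies 3 × 32 = 96 of 7 × 32 = 224 scheduled post-dose ECG timepoints (42.9%), and 96 of 11 × 32 = 352 vital-sign timepoints (27.3%).

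**Step 5. Absolute limits.** The absolute QTcF and vital-sign limits do not use the baseline value. However, SAP 17.4.1 classifies the worst QTcF after baseline, so a 12 h baseline could also leave the 2 h and 4 h values out of that classification.

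**The case against.** The best counter-argument is about how the sentence reads. The phrase about the last measurement can be taken to refer back to the one just defined, the last before treatment. The same-day clause would then only extend a pre-treatment baseline to a reading taken earlier on the dosing day. The contrast with adverse events and medications fits that reading.

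Other text points the same way:
- Protocol 8.2.3 compares each post-dose QTcF with baseline and calls for a prompt repeat, so a baseline must exist before the 2 h ECG.
- SAP Appendix 1 lists a Baseline visit ahead of Day 1.
- SAP 6.6 keeps data under their scheduled times.
- Protocol 8.10.2 puts dosing-day assessments before the dose by default.

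The output templates and derivation code are not available, the counts above are not effect sizes, and a 12 h change of exactly zero for everyone would probably be noticed.

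Most of this stands as evidence of intent, and pre-dose intent is the likelier reading. None of it puts a condition on the same-day rule. A measurement dated before the reference date cannot also coincide with it, so the clause must admit same-day values, and it does not say from which part of the day. The default in 8.10.2 exempts assessments that the schedule times otherwise, which covers the 2, 4 and 12 h readings. Appendix 1 governs display order only. A 2 h or 4 h baseline would not show itself by a zero change at 12 h. For ECG, even the favourable reading leaves the clause no scheduled value to apply to.

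**Conclusion.** The concern holds as a defect in the written rule. Followed literally, SAP 6.4 allows an on-treatment baseline for vital signs and, among scheduled ECGs on the dosing date, can select nothing else. Whether it was programmed that way cannot be told from the documents.

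The conclusion rests on Table 2 as printed, on morning dosing, and on readings taken close to schedule. No drug effect is assumed, so no ms or mmHg bias is claimed.

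The reach is limited to descriptive safety outputs. SAP 6.7 plans no tests. PK parameters, scheduled laboratory and weight baselines, and listed values are not affected. Using Day -1 throughout, as the general rule alone would do, would be a valid baseline, although it would pass over the Day 1 pre-dose vital signs. This should be fixed, but it does not threaten the primary objective.

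**What to change.** Replace the definition in SAP 6.4 with wording to this effect: baseline is the latest non-missing value obtained before study drug was given, judged by date and time or, where no clock time was recorded, by nominal timepoint (normally Day -1 for ECG and laboratory tests, Day 1 pre-dose for vital signs); no value obtained after dosing can serve as baseline. Then check the derivation code against it.

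The cost is one sentence and a code check, with no new data. SAP 15 treats dosing time as a data item. Because SAP 6.6 organises data by scheduled time, the nominal-timepoint fallback works even if ECG or vital-sign clock times are not on the eCRF, which the documents do not settle.

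An optional, separate improvement concerns SAP 17.4: where triplicate ECGs are taken, summarise the mean of the three tracings at that timepoint instead of the latest one. Protocol 8.2.3 already works with mean QTcF. The baseline finding does not depend on this.
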